## 5.6. Patients' discontinuations of treatment

Patients can discontinue the trial treatment for the following reasons:

- Unacceptable toxicity.
- Patients decline further treatment/therapy but accept to continue with protocol.
- Investigator's decision.

- Radiographic disease progression

After discontinuation of trial treatment, subsequent therapy decisions are left to the physician's discretion.

Patients who discontinue trial treatment will continue with the trial and the protocol-defined procedures, unless they specifically withdraw their consent and indicate that they do not want to perform any further trial-related visits or assessments (for patient withdrawals see Section 3.7).

## 5.7. Concomitant medications and therapies

All medications (including herbal preparations) and therapies taken by the patients or administered to the patients from the onset of trial and given in addition to the IP during the trial are considered as concomitant medications. Any concomitant medication(s) trial will be recorded in the eCRF.

### 5.7.1. Authorized concomitant treatments

All symptomatic treatments/therapies required for the patients' comfort (antiemetic, anti-diarrhoeic, antibiotics, and corticosteroid cream) are authorized with the exception of those treatments specified in Section 5.7.2 below. The posology and duration of administration are at the investigator's discretion, as per standard of care.

### 5.7.2. Prohibited concomitant treatments

Prohibited medication/class of drug:	Usage:
Any investigational anticancer therapy other than those under investigation in this trial	Should not be given concomitantly whilst the patient is on trial treatment
Any concurrent chemotherapy, radiotherapy, immunotherapy, or biologic or hormonal therapy for cancer treatment (prostate or second cancer) other than those under investigation in this trial	Should not be given concomitantly whilst the patient is on trial treatment. (Concurrent use of hormones for non-cancer-related conditions [e.g., insulin for diabetes and hormone replacement therapy] is acceptable. Local treatment of isolated lesions, excluding target lesions, for palliative intent is acceptable [e.g., by local surgery or radiotherapy])
CYP450 enzyme inducers	Use of strong CYP3A4 inducers and P-gp inducers (e.g., carbamazepine, phenobarbital, St. John's Wort) during treatment with darolutamide is not recommended, unless there is no therapeutic alternative. Selection of an alternate concomitant medicinal product, with no or weak potential to induce CYP3A4 or P-gp, should be considered.
BCRP substrates	Co-administration of darolutamide may increase the plasma concentrations of BCRP substrates (e.g., rosuvastatin, methotrexate, sulfasalazine, fluvastatin, atorvastatin). Therefore, the related recommendation in the product information of the BCRP substrate should be followed when co-administered with darolutamide.

Non-anticancer concomitant medication should be handled as recommended by the valid professional information for darolutamide unless otherwise specified in this protocol or the investigator brochure.

### **5.7.3. Drug-drug Interactions**

#### **5.7.3.1. Effects of other medicinal products on darolutamide**

##### **CYP3A4 and P-glycoprotein inducers**

Darolutamide is a substrate of CYP3A4 and P-glycoprotein (P-gp).

Use of strong and moderate CYP3A4 inducers and P-gp inducers (e.g. carbamazepine, phenobarbital, St. John's Wort, phenytoin, and rifampicin) during treatment with darolutamide is not recommended, unless there is no therapeutic alternative. Selection of an alternate concomitant medicinal product, with no or weak potential to induce CYP3A4 or P-gp should be considered.

Repeated administration of rifampicin (600 mg), a strong CYP3A4 and a P-gp inducer, with a single dose of darolutamide (600 mg) together with food, resulted in a decrease of 72% in mean exposure (AUC0-72) and a decrease of 52% in Cmax of darolutamide.

##### **CYP3A4, P-glycoprotein and breast cancer resistance protein inhibitors**

Darolutamide is a substrate of CYP3A4, P-gp and breast cancer resistance protein (BCRP).

No clinically relevant drug-drug interaction is expected in case of CYP3A4, P-gp or BCRP inhibitor administration. Darolutamide may be given concomitantly with CYP3A4, P-gp or BCRP inhibitors. Concomitant use of darolutamide with a combined P-gp and strong CYP3A4 inhibitor increases darolutamide exposure which may increase the risk of darolutamide adverse reactions. It is recommended to monitor patients more frequently for darolutamide adverse reactions and modify darolutamide dose as needed.

Administration of itraconazole (200 mg twice daily on day 1 and once daily on the following 7 days), a strong CYP3A4, P-gp and BCRP inhibitor, with a single dose of darolutamide (600 mg on day 5 together with food) resulted in a 1.7-fold increase in mean exposure (AUC0-72) and a 1.4-fold increase of Cmax of darolutamide.

##### **UGT1A9 inhibitors**

Darolutamide is a substrate of UGT1A9.

No clinically relevant drug-drug interaction is expected in case of UGT1A9 inhibitor administration.

Darolutamide may be given concomitantly with UGT1A9 inhibitors.

A population pharmacokinetic analysis showed that co-administration of UGT1A9 inhibitors with darolutamide resulted in a 1.2-fold increase in exposure (AUC0-72) of darolutamide.

#### **5.7.3.2. Effects of darolutamide on other medicinal products**

##### **Breast cancer resistance protein, organic anion transporting polypeptide substrates**

Darolutamide is an inhibitor of BCRP and organic anion transporting polypeptides (OATP) 1B1 and 1B3.

Co-administration of rosuvastatin should be avoided unless there is no therapeutic alternative. Selection of an alternative concomitant medicinal product with less potential to inhibit BCRP, OATP1B1 and OATP1B3 should be considered.

Administration of darolutamide (600 mg twice daily for 5 days) prior to co-administration of a single dose of rosuvastatin (5 mg) together with food resulted in approximately 5-fold increase in mean exposure (AUC) and  $C_{max}$  of rosuvastatin.

Co-administration of darolutamide with other BCRP substrates should be avoided where possible.

Co-administration of darolutamide may increase the plasma concentrations of other concomitant BCRP, OATP1B1 and OATP1B3 substrates (e.g. methotrexate, sulfasalazine, fluvastatin, atorvastatin, pitavastatin). Therefore, it is recommended to monitor patients for adverse reactions of BCRP, OATP1B1 and OATP1B3 substrates. In addition, the related recommendation in the product information of these substrates should be followed when co-administered with darolutamide.

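### Section 5.7.3.2 tells sites to replace rosuvastatin with a weaker transporter inhibitor, when the risk lies in being a substrate, and the Section 5.7.2 table is looser than Section 5.7.3 on the same drugs

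*Protocol*

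**What the plan says.** Section 5.7.3.2 of the protocol covers what darolutamide does to other drugs. Its subsection on BCRP and OATP substrates opens: "Darolutamide is an inhibitor of BCRP and organic anion transporting polypeptides (OATP) 1B1 and 1B3". It continues: "Co-administration of rosuvastatin should be avoided unless there is no therapeutic alternative". The next sentence advises on the replacement: "Selection of an alternative concomitant medicinal product with less potential to inhibit BCRP, OATP1B1 and OATP1B3 should be considered". The subsection then reports that darolutamide 600 mg twice daily for 5 days raised the AUC and Cmax of a single 5 mg dose of rosuvastatin about 5-fold. For the rest of the class it says: "Co-administration of darolutamide with other BCRP substrates should be avoided where possible". It names methotrexate, sulfasalazine and several statins, adds that "it is recommended to monitor patients for adverse reactions of BCRP, OATP1B1 and OATP1B3 substrates", and asks sites to follow the substrates' own product information as well.

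Section 5.7.3.1 covers the opposite direction, what other drugs do to darolutamide. The restriction there applies to "Use of strong and moderate CYP3A4 inducers and P-gp inducers", and the advice on a substitute is: "Selection of an alternate concomitant medicinal product, with no or weak potential to induce CYP3A4 or P-gp should be considered". On inhibitors it says: "Darolutamide may be given concomitantly with CYP3A4, P-gp or BCRP inhibitors".

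The table in Section 5.7.2 (Prohibited concomitant treatments) deals with the same drugs in two rows. The BCRP row lists rosuvastatin among its examples and asks only that the substrate's product information be followed. The inducer row restricts strong CYP3A4 inducers and P-gp inducers and recommends a substitute with little or no inducing potential.

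**The concern.** An instruction on choosing a substitute has to name the property that causes the problem. Here the co-medication is harmed because darolutamide blocks the transporters that handle it. A prescriber who follows the sentence literally would screen the replacement for inhibiting potential and could choose another substrate, which carries the same kind of risk.

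The second issue is that two consecutive sections give rules of different strength for the same drugs, and the protocol does not say which prevails. A site that consults only the 5.7.2 table would consider rosuvastatin acceptable under its label.

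What is at stake is patient safety, not inference. Section 1.2 lists polypharmacy among the burdens that some of these older men carry, and gives potential drug-drug interactions as one reason why enzalutamide or apalutamide is unsuitable for them. Because the trial is double-blind, investigators cannot adapt co-medication to the arm; they must apply the written rule to every patient.

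**Working it through.** No arithmetic applies. The check is a side-by-side reading.

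**Step 1: which drug acts and which is affected.**
- Acting drug: darolutamide, stated to inhibit BCRP, OATP1B1 and OATP1B3 (5.7.3.2, first line).
- Affected drug: rosuvastatin, whose exposure rises about 5-fold (5.7.3.2). The subsection heading concerns substrates.
- It follows that risk depends on how far the co-medication relies on these transporters. Its own capacity to inhibit them plays no part in the effect described.

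**Step 2: compare the parallel sentence in 5.7.3.1.** For inducers the roles are the other way round: the co-medication acts and darolutamide is affected. Asking for a substitute with weak inducing potential is therefore right there. The 5.7.3.2 sentence has the same form, but the direction of the interaction is reversed, so the property should change from acting on the transporter to being carried by it.

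**Step 3: is inhibition by the co-medication a concern elsewhere?** For BCRP, 5.7.3.1 says not: "Darolutamide may be given concomitantly with CYP3A4, P-gp or BCRP inhibitors". It makes no statement about OATP1B1 or OATP1B3 inhibitors, so it supports the reading for BCRP only. Step 1 is enough without it.

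**Step 4: compare the 5.7.2 table with 5.7.3.**

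| Drug or class | 5.7.2 table | 5.7.3 |
|---|---|---|
| Rosuvastatin | Named as an example; follow its product information | Avoid if any alternative exists |
| Other BCRP substrates | Follow product information | Avoid where feasible, monitor, and follow product information |
| OATP1B1/1B3 substrates | Not mentioned | Monitor and follow product information; pitavastatin is named only here |
| CYP3A4 inducers | Strong | Strong and moderate |

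The first row is a difference in the rule itself: the table permits what 5.7.3.2 tells sites to avoid. The second, third and fourth rows are places where the table is less complete.

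**Step 5: does any other clause settle the difference?** The closing line of 5.7.2 defers to the darolutamide product information unless the protocol or the investigator brochure specifies otherwise. For rosuvastatin and other BCRP substrates the protocol specifies two rules of different strength, so that line cannot choose between them. For OATP1B1/1B3 substrates and moderate inducers the table is silent and 5.7.3 is the only explicit rule. Those two are gaps in the table and not conflicts.

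**The case against.** The strongest reply is that the faulty sentence is unlikely to mislead anyone. The heading says substrates, the opening line names darolutamide as the inhibitor, the preceding sentence says to avoid rosuvastatin, and the following paragraphs name the other statins, advise avoidance and ask for monitoring. This stands, and it is why the effect is limited. It does not make the sentence correct.

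A second reply is that only the rosuvastatin row is a true contradiction. For other BCRP substrates, following product information is part of what 5.7.3.2 asks, so a site can satisfy both sections. Pitavastatin is missing only from a list of examples. The table's advice on a substitute for inducers already rules out a moderate inducer as the replacement. These points are fair: the last three rows show incompleteness, not opposite instructions. The inducer advice, however, applies only once a drug has been flagged for replacement, and the table does not flag a moderate inducer already in use.

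A third reply concerns how a site would come to rely on the table. Section 5.7.1 sends readers to 5.7.2 for exceptions, but it concerns treatments for patient comfort, and a statin or methotrexate is not obviously among them. Section 5.7.3 also follows directly under its own heading. This is accepted: the cross-reference in 5.7.1 is weak evidence that a prescriber would stop at the table. Likewise, the protocol lists polypharmacy as one of several possible problems in older men and does not say it is universal.

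None of these replies touches the two central facts: the wrong property in 5.7.3.2 and the looser rosuvastatin rule in 5.7.2.

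**Conclusion.** The concern holds. One sentence in 5.7.3.2 names the wrong pharmacological property, and the 5.7.2 table falls short of 5.7.3 on four points, one of which (rosuvastatin) is a substantive disagreement. The conclusion rests only on the protocol's own statement of which drug inhibits and which is affected.

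The only exposure figure given for this transporter interaction is the approximately 5-fold rise for rosuvastatin. None is given for other statins, and none for moderate inducers. The number of patients affected cannot be derived, and none is claimed. Harm is possible only where a site relies on the table or on the single sentence alone. There is no effect on the endpoint, type I error, power or sample size. It is a minor correction, but one that should be made, because the text is an operative prescribing instruction.

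**What to change.** Reword the sentence in 5.7.3.2 along these lines: *Consider a replacement that is not a substrate of BCRP, OATP1B1 or OATP1B3, or is a weaker one.*

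Bring two rows of the 5.7.2 table into line with 5.7.3, using the stricter rule already there:
- **Transporter row:** extend it to OATP1B1 and OATP1B3 substrates and add pitavastatin to the examples. State that rosuvastatin is to be avoided if any alternative exists and that other BCRP substrates are to be avoided where feasible. If a BCRP, OATP1B1 or OATP1B3 substrate is given, patients should be monitored for its adverse reactions and its product information followed.
- **Inducer row:** restrict moderate as well as strong CYP3A4 inducers, together with P-gp inducers, unless no alternative exists.

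The cost is one sentence and two table rows in the next amendment, with no change to data collection, analysis or sample size. It is still worth doing: the current amendment reports about 115 of 300 patients enrolled, which leaves about 300 − 115 = 185 to enter, and treatment continues until radiographic progression.

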### **P-gp substrates**

No clinically relevant drug-drug interaction is expected in case of P-gp substrate administration. Darolutamide may be given concomitantly with P-gp substrates (e.g. digoxin, verapamil or nifedipine). Co-administration of darolutamide together with the sensitive P-gp substrate dabigatran etexilate did not reveal any increase in exposure (AUC and  $C_{max}$ ) of dabigatran.

### **CYP3A4 substrates**

Darolutamide is a mild inducer of CYP3A4.

No clinically relevant drug-drug interaction is expected in case of CYP substrate administration. Darolutamide may be given concomitantly with CYP substrates (e.g. warfarin, L-thyroxine, omeprazole).

Administration of darolutamide (600 mg twice daily for 9 days) prior to co-administration of a single dose of the sensitive CYP3A4 substrate midazolam (1 mg) together with food, decreased the mean exposure (AUC) and  $C_{max}$  of midazolam by 29% and 32%, respectively.

Darolutamide did not inhibit the metabolism of selected CYP substrates *in vitro* at clinically relevant concentrations.

### **Medicinal products that prolong the QT interval**

Since androgen deprivation treatment may prolong the QT interval, the co-administration with medicinal products known to prolong the QT interval or medicinal products able to induce Torsades de pointes should be carefully evaluated. These include medicinal products such as class IA (e.g. quinidine, disopyramide) or class III (e.g., amiodarone, sotalol, dofetilide, ibutilide) antiarrhythmic medicinal products, methadone, moxifloxacin, and antipsychotics (e.g. haloperidol).

#### **5.7.4. Treatment at radiographic disease progression**

Following radiographic progression, subsequent treatment will be prescribed at the investigator's discretion.

#### **5.7.5. Contraception during the trial**

Non-sterilized males who are sexually active with a female partner of childbearing potential must use a male condom plus spermicide during the treatment phase and for 2 weeks after the last trial treatment administration. Male patients should refrain from sperm donation throughout this period.

## Definitions

Females of childbearing potential are those who are not surgically sterile (i.e., bilateral tubal ligation, bilateral oophorectomy, or complete hysterectomy) or post-menopausal (for the definition of post-menopausal see below).

Women will be considered post-menopausal if they have been amenorrhea for 12 months without an alternative medical cause. The following age-specific requirements apply:

- Women <50 years of age would be considered post-menopausal if they have been amenorrhea for 12 months or more following cessation of exogenous hormonal treatments and if they have luteinizing hormone and follicle-stimulating hormone levels in the post-menopausal range for the institution or underwent surgical sterilization (bilateral oophorectomy or hysterectomy).
- Women ≥50 years of age would be considered post-menopausal if they have been amenorrhea for 12 months or more following cessation of all exogenous hormonal treatments, had radiation-induced menopause with last menses >1 year ago, had chemotherapy-induced menopause with last menses >1 year ago, or underwent surgical sterilization (bilateral oophorectomy, bilateral salpingectomy or hysterectomy).

## 6. EVALUATION OF TREATMENT EFFICACY AND SAFETY

### 6.1. Efficacy evaluation

Treatment efficacy will be evaluated by measuring changes in tumour size/number of lesions (see Section 7.3.8) and serum PSA levels in response to treatment; according to PCWG3 criteria ([Scher, 2016](#); Appendix 3).

Patient's disease will be assessed at "baseline" (during the screening period) and then every 120 (±14) days after randomisation during the first 2 years and every 180 (±14) days thereafter, until documented radiographic progression, or death, whichever occurs first. For patients who discontinue study treatment for reasons other than radiographic progression, death, or consent withdrawal, investigators will continue to perform disease evaluations during the follow-up period until progression.

The primary evaluation endpoint is radiographic progression-free survival, defined as time from randomisation to radiographic progression according to PCWG3 criteria or death, whichever occurs first.

For secondary evaluation endpoints see Section 3.2.2.

#### 6.1.1. Centralized review

The final analysis of the primary endpoint (rPFS) will be analysed according to the investigators' assessment of response. If the results meet the pre-specified hypothesis (see Section 10.1), an additional sensitivity analysis of rPFS will be performed using the results of a centralised disease evaluation by an independent review committee (IRC).

The IRC will be provided with recordings of each scheduled CT scan or magnetic resonance imaging (MRI) exam (DICOM format), bone scan, and any other clinical, biological, or radiographic disease assessments performed. Disease evaluation will be performed according to the schedule and methods described in a separate IRC charter.

**Note:** Treatment decisions are to be made by the investigator, based on their assessment of patient response.

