## 3.2. Trial Endpoints

### 3.2.1. Primary endpoint

Radiographic progression-free survival, defined as time from randomisation to radiographic progression as assessed by the investigator according to PCWG3 criteria ([Scher, 2016](#); Appendix 3), or death, whichever occurs first.

*According to the PCWG3 recommendations; radiographic progression is defined as either the appearance of two or more new bone lesions on bone scan or a nodal or visceral progression according to Response Evaluation Criteria in Solid Tumours version 1.1 (RECIST v1.1; [Eisenhauer, 2009](#)). The date of radiographic progression will be the date of the first reported event meeting the above definition (see Appendix 3 & Appendix 4 for further details).*

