### 7.3.8. Disease evaluation

Disease evaluation should be performed every 120 ( $\pm 14$ ) days during the first two years after the initiation of study treatment and then every 180 ( $\pm 14$ ) days until treatment discontinuation. Additional radiographic disease evaluations should also be performed if clinical symptoms indicate a need for radiographic confirmation of disease progression.

**Note:** Changes to the patient's treatment schedule (e.g. treatment interrupted due to toxicity) should not affect the schedule of tumour evaluations: these should continue to be performed every 120 or 180 ( $\pm 7$ ) days as planned.

The following will be performed at each disease evaluation:

- Clinical assessment of palpable or visual lesions.
- Measurement of serum PSA and testosterone levels.
- CT scan or MRI (for measurement of target lesions)
- Bone scan.
- Documentation of response assessment according to PCWG3/RECIST v1.1 (including documentation of size/status of each measurable and non-measurable lesion; see Appendix 3 & Appendix 4).

**Note:** The same diagnostic method(s) must be used to evaluate disease status throughout the study.

*According to PCWG3 recommendations, the recommended imaging examinations for disease assessment are as follows: CT Scan or MRI (to assess Visceral lesion/lymph nodes) and Bone scan (to assess bone lesions). If bone scan is not available, PET scan or plain films can be used to confirm the presence or disappearance of bone lesions. Please refer to appendix 3 - The Prostate Cancer Working Group 3 – Recommendations for castration-resistant prostate cancer trials.*

Other appropriate radiographic assessment (e.g. 11C-, FCH-, or FDG-labelled PET/CT, ultrasonography), to be performed at the investigator's discretion.

*The results of all radiographic assessment (DICOM format) must be provided for central review by the IRC (Section 6.1.1).*

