#### 7.4. End-of-treatment visit

Patients will continue to receive study treatment and undergo study procedures as outlined above until radiographic disease progression. Study treatment will be continued for subjects who have increasing PSA values in the absence of radiographic or clinical progression. Although serial PSA measurements will be performed in this study, progression or change in PSA values is not considered a reliable measure of disease progression and should not be used as the lone indicator for discontinuation.

In case of clinical progression without radiographic progression, the investigator should also assess whether it is the patient's best interest to stop study treatment and change to another therapy, or in selected cases, to carry on with the study treatment.

Treatment may also be terminated early at the initiative of either the patient or the investigator for any reason that would be beneficial to the patient, including: unacceptable toxicity, intercurrent conditions that preclude continuation of treatment, or patient request.

If the study treatment is terminated, the ADT should be continued.

Following treatment discontinuation for any reason, the following examinations are to be performed 30 ( $\pm$  3) days after last dose of study treatment, or before initiating a new antineoplastic therapy, whichever comes first:

- Complete clinical examination (major body systems).
- Collection of height and body weight.
- Measurement of vital signs (blood pressure, seated heart rate, body temperature).
- Assessment of ECOG performance status.
- Electrocardiogram (only in case of abnormal results at screening visit, or if clinically indicated by patient symptoms)
- Assessment of ongoing toxicities including pre-existing symptoms and any concomitant therapies received.
- Haematology analysis (see Table 3, page 47).
- Serum chemistry (see Table 3, page 47).
- Measurement of serum PSA and testosterone levels.
- Assessment of patient quality of life using the following tools:
  - EORTC-QLQ-C30 (Appendix 10)
  - EORTC-QLQ-PR25 (Appendix 11)
  - BPI-SF (Appendix 12)

- Assessment of patient geriatric status using the G-CODE assessment tool (Appendix 8).
- **For patients who provide additional informed consent:** Where medically feasible a biopsy should be performed at time of disease progression to collect a treatment-resistant tumour sample.

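### The central re-read of rPFS is supplied with PSA and clinical data that the imaging endpoint does not use; the protocol should have radiographic progression read masked to them

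*Protocol*

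**What the plan says.** Under Section 6.1.1 the primary rPFS analysis "will be analysed according to the investigators' assessment of response". If that result meets the prespecified hypothesis, "an additional sensitivity analysis of rPFS will be performed using the results of a centralised disease evaluation by an independent review committee (IRC"). The same section lists what the committee is given: the scheduled CT or MRI recordings, "bone scan, and any other clinical, biological, or radiographic disease assessments performed". It then adds: "Disease evaluation will be performed according to the schedule and methods described in a separate IRC charter". That charter is not among the documents.

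Section 7.3.8 lists the components of each disease evaluation, among them "Measurement of serum PSA and testosterone levels". Its closing note on central review speaks of images only: "The results of all radiographic assessment (DICOM format) must be provided for central review by the IRC (Section 6.1.1"). Section 7.1 carries an equivalent note for the screening images.

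For the primary endpoint, Section 3.2.1 says that "radiographic progression is defined as either the appearance of two or more new bone lesions on bone scan or a nodal or visceral progression" by RECIST v1.1; death also counts as an event. Section 7.4 says that "progression or change in PSA values is not considered a reliable measure of disease progression".

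**The concern.** A central re-read is worth having because it can disagree with the investigator for reasons that do not share the investigator's possible biases. Investigators measure PSA at every scheduled visit from Day 30. An equivocal scan is more likely to be called progression when PSA is rising and stable when PSA is suppressed. Darolutamide is an androgen-receptor antagonist (Section 1.1.3), Section 6.1 uses PSA as a measure of efficacy, and complete PSA response at 6 months is a secondary endpoint. A PSA difference between arms is therefore what the trial expects. No one has to be unblinded for this to matter: PSA need only differ by arm and sway some reads.

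If the IRC holds the same PSA values, it is open to the same pull. What is at stake is how much reassurance the IRC analysis can give about a positive investigator-based result. The result itself does not depend on the IRC.

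**Working it through.** No figure in the plan bears directly on this point, so the main check sets the sections side by side.

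**1. Is PSA in the IRC package?** Section 6.1.1 covers biological disease assessments without naming PSA. Section 7.3.8 makes PSA and testosterone part of every disease evaluation. On a plain reading they are included. The notes in 7.1 and 7.3.8 speak only of radiographic results in DICOM format, so the protocol describes the IRC material in two different scopes.

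**2. Does calling progression need PSA?** No. Section 3.2.1 and Appendix 3 define radiographic progression by new bone lesions or RECIST nodal or visceral progression. The tumour-marker conditions in Appendix 4 concern complete response, and non-CR/non-PD, of non-target lesions. Neither governs progression.

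**3. Does another IRC task need PSA?** None is stated. Castration resistance in Appendix 3 uses PSA, but Section 10.3.2 has the secondary endpoints analysed on investigator assessment.

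**4. Is there another re-read of the scans?** No. The other rPFS sensitivity analysis in Section 10.3.2 censors at the start of a subsequent therapy and leaves the investigator's reading as it is.

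**5. How far could PSA point to the arm?** The documents give no PSA response rates by arm, so this is assumption only. With 1:1 allocation, suppose a reader guesses darolutamide when PSA is at or below 0.2 ng/ml at 6 months and placebo otherwise. With response rates p_D and p_C, the probability of a correct guess is ½·p_D + ½·(1 − p_C) = 0.5 + (p_D − p_C)/2.

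| Assumed p_C | Assumed p_D | Correct guesses |
|---|---|---|
| 20% | 20% | 50% |
| 20% | 40% | 60% |
| 20% | 60% | 70% |
| 10% | 60% | 75% |

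Under such rates PSA would be suggestive of the arm, not decisive.

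**6. What could it do to the IRC estimate?** An illustrative simulation had no true effect and 1,500 trials per setting.

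- From the protocol: 300 patients, accrual as in Section 10.1, control median 12 months, drop-out hazard 0.014 per month, scans every 120 days for two years and every 180 days afterwards, and a log-rank test at 197 events with |Z| > 2.0.
- Assumed: 25% of events are deaths; PSA starts rising at a median of 8 months (control) and 16 months (darolutamide); 10-20% of scans before true progression are equivocal.

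| Reading of equivocal scans | IRC hazard ratio | False result favouring darolutamide |
|---|---|---|
| Called progression 40% of the time whatever the PSA | 1.005 to 0.998 | 1.9% to 2.7% |
| Called 60-80% of the time if PSA is rising, 20% otherwise | 0.964 to 0.927 | 4.1% to 6.3% |

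The nominal one-sided rate at Z = 2.0 is 0.0455/2 = 2.3%. The Monte Carlo standard error near 5% is √(0.05 × 0.95/1500) = 0.6 percentage points. The direction is clear and the shift is small beside the design hazard ratio of 0.65. The simulation omits the bone-scan confirmation described in Appendix 3.

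**The case against.** The strongest reply is that receiving data is not the same as using it. The reading method sits in a charter that is not shown and may already prescribe an image-first read with clinical data held back. This stands in part. However, Section 6.1.1 leaves schedule and methods to the charter and itself fixes the material supplied, and it requires no masked read.

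A reader might infer that the IRC is effectively unblinded, or is not independent at all. The documents do not support that. The trial is double-blind and placebo-controlled, both arms receive ADT, no PSA rates by arm are given, and nothing hands the IRC the allocation or, in terms, the investigator's call. The committee still reads the images itself; only some of its information overlaps with the investigator's.

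A reader might also infer that the IRC is the plan's only protection against biased reading. It is the only second read, but placebo blinding, the numerical progression thresholds and bone-scan confirmation in Appendix 3, and the structured bone-scan form in Appendix 13 all help.

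The simulated 4-6% might be taken as inflation of the trial's type I error. It is not. It is an unconditional rate for an analysis that runs only after the primary analysis has succeeded and that does not decide the trial.

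Finally, some non-CT data are legitimate inputs to the read. Sections 7.1 and 7.3.8 and Appendix 3 allow PET or plain films where bone scan is unavailable, Appendix 4 accepts calliper measurement, and 7.3.8 assesses palpable lesions. An instruction to send CT/MRI and bone scans alone would go too far. That objection stands in full and shapes the fix.

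**Conclusion.** The point holds as a cheap improvement. The protocol supplies the IRC with PSA and clinical data that its one stated task does not require for calling progression, describes the IRC material more narrowly in 7.1 and 7.3.8, and states no masked read. Agreement between the IRC and investigator analyses therefore could not exclude PSA-influenced reading of equivocal scans. This rests on two premises: that biological disease assessments include PSA, and that PSA will differ by arm. The first follows from Section 7.3.8. The second is a reasonable expectation without figures in the documents. The size of any bias cannot be derived from the documents, and the simulated shift to 0.96-0.93 illustrates direction only. The primary analysis, alpha, the 197-event target and the sample size are unaffected.

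**What to change.** Amend Section 6.1.1, and align Sections 7.1 and 7.3.8 and the IRC charter, along these lines:

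*The IRC will determine radiographic progression from all dated protocol imaging (CT/MRI, bone scan, and PET or plain films where used instead), lesion measurements from clinical examination, and the dates and sites of local treatment. The read will be masked to PSA, testosterone, symptoms, investigator reads and treatment status. Dates of death will be added at analysis.*

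If the charter already prescribes such a read, 6.1.1 should say so and the three sections should be reconciled.

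The cost is a few sentences and the work of separating the masked items from the IRC package. No additional reader, scan or visit is needed. About 115 of 300 patients were enrolled at this amendment and the IRC analysis follows the primary one, so the change can be in place well before any central result is used.
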